5.2 Handling of Study Interventions

Mouth rinses will be acquired from the following sources:

mouth rinse*	Source: Online pharmacies and reputable marketplaces with over the counter mouth rinses
26.9% ethanol plus essential oils	Listerine's Original Mouth rinse- Amazon or CVS online store
0.1% Cetylpyridinium Chloride	Crest Pro-Health Mouth rinse- Amazon or CVS online store
Sterile water	Amazon or CVS online store

**All mouthrinses are commercially available in the USA, routinely used in clinical settings, and will be used in an on-label manner.*

Any adverse events or protocol deviations will be reported to the UNC IRB. Weekly meetings of the internal quality control committee will allow us to closely monitor such events.

5.3 Concomitant Interventions

There are no concomitant interventions other than the mouth rinse and a short survey.

5.3.1 Allowed Interventions

There are no additional interventions, other than mouth rinsing with one of the 3 options previously described. If patients have an allergic reaction, EMS will be contacted for management and emergency medical procedures will be followed until EMS arrives. If a patient begins experiencing anaphylaxis, we will administer epinephrine via an epi-pen, as a rescue medication. No other rescue medications are indicated.

5.3.2 Required Interventions

The patient will rinse with a blinded mouth rinse for 60 seconds and then will spit it out, followed by donating saliva samples.

5.3.3 Prohibited Interventions

Patients who have drank or eaten within an hour of the study visit will be excluded.

Patients who have consumed alcohol within 12 hours of the study visit.

Patients who have used a mouth rinse within 24 hours of the study will be excluded.

Patients who have participated in a study of other oral products (toothpaste, mouth rinses) within the prior 30 days will be excluded.

Patients who are abusers of alcohol or recreational drugs.

5.4 Adherence Assessment

Adherence would be defined as rinsing with the mouth rinse for a full 60 seconds before expectorating, and then providing a baseline saliva sample followed by saliva samples every 15 minutes four times, until an hour post-rinse (15 min, 30min, 45min, 60min).

6. STUDY PROCEDURES

6.1 Schedule of Evaluations

Assessment	Phone Screening: (Day-14 to Day -1)	Final Screening, Baseline, Enrollment, Randomization, Intervention: Visit 1 (Day 0)
Informed Consent Form	Provided for review	X
Demographics		X
DXA	X verbally asked	X
Medical History		X
Current Medications		X
Rapid Antigen Test-COVID+		X

Urine Analysis- pregnancy		
Vital Signs		
Inclusion/Exclusion Criteria	 reviewed	
Enrollment/Randomiz- ation		
Treatment Administration Form		
Concomitant Medications		
Adverse Events		

6.2 Description of Evaluations

Subjects are required to be onsite for a 70-90 minute, single visit appointment. After consenting and confirmation of meeting inclusion/exclusion criteria, subjects will be asked to rinse with an unlabeled/blinded antiviral mouth rinse for 60 seconds and provide 5 mL of saliva prior to the rinse and 2 mL of saliva immediately post-rinse, 15 minutes post-rinse, 30 minutes post-rinse, 45 minutes post-rinse, and 60 minutes post-rinse. Subjects will also be asked questions as part of a short survey about the rinsing experience and their willingness to rinse in different situations.

6.2.1 Screening Evaluation

Consenting Procedure

Patients will be contacted first by phone and, if not available, then by email. The consent process will be conducted by a study coordinator. The study's purpose and requirements will be explained and the patient will have the opportunity to ask questions and will have time to consider participation. Interested patients will make an appointment to visit the Go Health Clinical Research Unit at Adams School of Dentistry for this study. Study participation includes only one visit. The consent forms will be reviewed and signed by interested patients in person in the clinical isolation unit associated with the Go Health Clinical Research Unit at Adams School of Dentistry prior to study participation. For Spanish speaking patients and/or parents, Spanish forms will be provided and

communication will occur through a Spanish translator. For hospital in-patients appearing on the EPIC COVID+ list, subjects will be approached by a study coordinator in their private room. The study's purpose and requirements will be explained and the patient will have the opportunity to ask questions and will have time to consider participation. If interested, consent forms will be left in the patient's room for review. Study team members will return later for final consent signatures and if consenting, the study visit can occur in their hospital room. All patients are adults and have normal cognitive capacity, and therefore will be able to consent for themselves.

Screening

PreScreening is typically done through a phone call but may be supplemented with email correspondence. The screening process is finalized at Visit 1.

- During the prescreening conversation the patient will answer screening questions regarding inclusion and exclusion criteria and will be provided with the informed consent to read and review prior to consenting and enrollment process.

At the visit, participants lacking a lab or physician confirmed COVID+ test will be administered a rapid antigen test by study personnel at the time of their visit to confirm their COVID infection. Any participants that produce a negative rapid antigen test (on-site) will be excluded. Next, women participants of childbearing potential will be asked to provide a urine sample in the restroom, to undergo a rapid pregnancy test by study personnel. Any pregnant or lactating patients will be excluded. If a participant meets enrollment criteria and consents to participate, their answers will be entered into the CDART research database managed by UNC.

6.2.2 Enrollment, Baseline, and/or Randomization

Enrollment

Outpatient subjects will be recruited from patients seen in the UNC Respiratory Diagnostic Clinic (RDC), UNC testing sites or UNC hospital who have tested positive for COVID-19. Subjects will be contacted for recruitment by phone and (if unreachable by phone) by secure email by study personnel; patients will have the study rationale and risks explained and will be provided time to ask questions and consider participation. If patients are interested in participating, a single appointment will be scheduled for them at the Adams School of Dentistry Go Health Clinical research core in the associated clinical research isolation area. Consent documentation will be signed in person and in private in the Clinical Research Core. A list of COVID+ subjects will be provided by the RDC clinic and EPIC, accessible via secure UNC servers or secure UNC email to our research team's clinical coordinator, and this list will include names and contact details (PHI). This list is updated daily and provided to approved research sites, including ours.

Baseline Assessments

Study personnel confirm enrollment qualifying criteria and perform a COVID rapid antigen test and pregnancy test on applicable individuals. Otherwise, there are no baseline assessments required as this study only requires a 70-90 minute single visit appointment.

Randomization

Our statistician will create a block randomization tool which will be provided to the unblinded study staff ([name]) to perform the randomization. In the instance that [name] is unavailable, [name] or [name] will perform randomization and set-up the rinses. The participant's group assignment will be communicated to the blinded clinical staff. All patients will be consented and then complete our screening questions for inclusion and exclusion to confirm eligibility prior to being assigned to the randomization schedule.

The researcher in charge of collecting the salivary samples will be blinded to the mouthwash solution, as they will be given a pre-aliquoted mouth rinse in an unlabeled storage tube to provide to the patient for the rinse.

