Participants will be asked to give a baseline salivary sample (5ml over 5 minutes) and then asked to rinse with an unlabeled (blinded) antiseptic mouth rinse for 60 seconds according to the table below. The rinses and control will be similar in appearance visually, such that a double-blind can be maintained. The research assistant ([name]) will be the sole unblinded staff member who will perform randomization and communicate the subject's group assignment to blinded study staff, in advance of the visit based on the block randomization schedule. The unblinded staff member will set-up the rinses for the participants appointment minimizing the possibility of study staff being able to identify the blinded rinses. In the instance that [name] is unavailable, [name] or [name] will perform randomization and set-up the rinses. Blind will be strictly maintained except in the case of medical emergency requiring reveal of an individual's rinse identity. The product group key will be provided to the analyzing statistician at the conclusion of the clinical study.

mouth rinse*	Number of participants (sample size)	Group
26.9% ethanol plus essential oils	84	Experimental
0.1% Cetylpyridinium Chloride	84	Experimental
Sterile water	84	Control

**All mouth rinses are commercially available in the USA, routinely used in clinical settings, and will be used in an on-label manner.*

After the participant expectorates the mouth rinse, research staff will collect another salivary sample (T_0 , 2 mL over 5 minutes). During a 10 minute recuperation period, the study participants will answer demographics survey questions and questions regarding the taste, color, flavor and general acceptability of using the mouth rinse as part of routine dental and medical visits as well as in social settings. At 15 minutes post-rinse, the participant will be asked to provide an additional saliva sample (2 mL over 5 minutes), followed by another 10 minute recuperation period. This sequence will be repeated for at

the 30, 45 and 60-minute time points post rinse. At 60 minutes, the study participant will give their final salivary sample (2 mL over 5 min), and study participation will conclude.

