9.2 Sample Size and Randomization

Based on similar viral infectivity studies evaluating antiviral mouth rinse efficacy, we were able to run power calculations to estimate effect size and determine sample size as a function of length of mouth rinse time course. The sample size is justified by a paired t-test on outcomes between time points. With simultaneous comparisons, the sample size n=43 for each mouth rinse can detect the effect size in Cohen's $d = 0.8$ at 30 minutes, which is between medium and large, under 80% power and 0.016 type-I error rate by Bonferroni correction.¹² To account for 14% of patients having no virus in their saliva and 10% of patients producing insufficient saliva, we plan to enroll 55 participants per arm.

The statistical consultant on this project will create a block randomization tool for the study staff; the unblinded staff member will randomize a participant once enrollment compliance has been confirmed and consent has been given. The participant's group assignment will then be communicated to the blinded study staff. IRB approved study personnel will ask participants screening questions to confirm eligibility for enrollment. After consent and screening, the randomization tool will be used by study staff to assign the subject to a study group.

The researcher responsible for collecting the salivary samples will be blinded to the mouthwash solution, as they will be given a pre-aliquoted mouth rinse in an unlabeled tube to provide to the patient for the rinse.

The PI, Co-I, study coordinators and study personnel who work for GoHealth are authorized to break the blinding based on emergency medical necessity such as if a patient suffers an allergic or adverse reaction to one of the mouth rinses. Though highly unlikely as all mouth rinses are sold commercially at Walgreens and CVS, adverse or allergic reactions are possible. Using the numerical code associated with the participant and mouth rinse syringe, the study personnel responding to the emergency can reference the block randomization schedule to determine the mouth rinse type, to inform the emergency medical workers, poison control or the emergency room what type of mouth rinse product led to the reaction.

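### The plan tells the unblinded person to pass each participant's group assignment to the blinded staff before the rinse, and never says in what form

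*Combined protocol and SAP*

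**What the plan says.** Three sections describe the hand-over of the allocation.

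- Section 3 (Study Design): one research assistant "will be the sole unblinded staff member". This person randomises and communicates the "group assignment to blinded study staff, in advance of the visit based on the block randomization schedule". Two further people may randomise and set up rinses when that person is away.
- Section 6.2.2 (Randomization): the participant's "group assignment will be communicated to the blinded clinical staff".
- Section 9.2: once consent and eligibility are settled, the "group assignment will then be communicated to the blinded study staff".

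Other passages bear on what this means.

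- Section 6.2.2 says that the person collecting saliva "will be blinded to the mouthwash solution, as they will be given a pre-aliquoted mouth rinse in an unlabeled storage tube". Sections 6.2.3 and 9.2 say much the same.
- Section 3 states that "The product group key will be provided to the analyzing statistician at the conclusion of the clinical study".
- Section 9.2, on emergency unblinding, has staff consult the randomisation schedule: "Using the numerical code associated with the participant and mouth rinse syringe".
- On matching, Section 3 says: "The rinses and control will be similar in appearance visually, such that a double-blind can be maintained". The products are 26.9% ethanol with essential oils, 0.1% cetylpyridinium chloride, and sterile water.
- Taste, colour and flavour questions come in the break after the immediate post-rinse (T0) sample (Sections 3 and 5.1). Section 10.1 has study personnel ask the questions and enter the answers.
- Staff collecting samples record insufficient volume and whether a participant must be withdrawn and replaced (Section 10.3.3).
- Laboratory samples carry only alphanumeric identifiers (Section 3, sample processing).

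**The concern.** Group assignment is the item that masking exists to withhold, and the plan directs that it be given to the people it calls blinded. They have no stated need for it: Section 3 has the unblinded person set up the rinse, and the collector receives it already measured out.

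Without a shared code, a remark such as that the rinse tastes of water unmasks one participant, after that participant has rinsed. With a shared code, the same remark can carry over to everyone later assigned to that code. Staff could then know the arm while taking the baseline sample, supervising the 60-second rinse, collecting the T0 sample and deciding whether a participant who produces too little saliva is removed and replaced. Removal and replacement occur after randomisation, so handling that differed by arm would change who is analysed.

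The staffing text adds a smaller gap. The unblinded person is called the only one, but two others may do the same work, and no section says that they then stay away from blinded duties.

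**Working it through.** The plan gives no figure on this point, so there is nothing to reproduce. The check has two parts.

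**1. What could the communicated assignment be?**

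| Possible meaning | Support in the documents | Effect on masking |
|---|---|---|
| Product name | The literal sense of an assignment; conflicts with holding back the product group key | Lost at once |
| Experimental or Control | Group column of the table in Section 3 | Active versus water known at once |
| Code shared by an arm | Suggested by the product group key in Section 3; not stated | Can be learned from taste reports |
| Number unique to the participant | A possible reading of the code in Section 9.2 | Safe, but it would not be a group assignment |

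Three of the four readings are harmful, and the text does not choose among them. The timing differs between Section 3 (before the visit) and Section 9.2 (after consent and screening), but under both the information arrives before the rinse and every sample.

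**2. How far could a shared code spread?**

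Inputs:
- Arm size n = 84 (Précis and Section 3) or n = 55 (Sections 2.2, 9.1, 9.2 and 9.5). The documents conflict, so both are used.
- q, the chance that one participant's report reveals the rinse. The documents give no value; it is assumed and varied.
- Codes fixed for the whole trial, and every revealing report noticed, remembered and shared among the blinded staff. These are also assumptions.

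The i-th participant in an arm is sampled with the code still unknown only if none of the i − 1 earlier participants revealed it, which has probability (1 − q)^(i−1). Summing over the arm:

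expected number sampled before the code is known = [1 − (1 − q)^n] / q

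share sampled after the code is known = 1 − [1 − (1 − q)^n] / (n q)

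For q = 0.1:
- n = 84: 0.9^84 ≈ 0.0001, so the share is 1 − 0.9999/8.4 = 0.881.
- n = 55: 0.9^55 ≈ 0.0030, so the share is 1 − 0.9970/5.5 = 0.819.

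| q | n = 84 | n = 55 |
|---|---|---|
| 0.1 | 88.1% | 81.9% |
| 0.25 | 95.2% | 92.7% |
| 0.5 | 97.6% | 96.4% |
| 1 | 98.8% | 98.2% |

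The formula treats each arm alone. Two recognised codes would give the third by elimination, which is not counted here. If staff held only a participant-unique number, an earlier report would carry nothing forward and exposure through the code would be zero.

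**The case against.** A reader might infer that the people collecting saliva are certainly told a code for the arm, so that one taste report unmasks the rest of that arm before they arrive. The documents do not support that.

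- The recipients are blinded clinical or study staff. That the saliva collector is among them is an inference, and the plan says more than once that the collector is blinded to the solution. It stands only in that nothing exempts the collector.
- A shared code is also an inference. The sentence about the product group key concerns the analysing statistician, and the code in Section 9.2 may be specific to the participant.
- Knowledge before arrival follows only from Section 3. Under Section 9.2 the assignment is released after consent and screening.
- The percentages rest on an assumed q and on perfect sharing of information among staff. They say nothing about the size of any effect on an endpoint.

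Existing safeguards also count. The primary outcomes are laboratory assays on samples with alphanumeric labels. Saliva volumes have fixed targets (5 mL, then 2 mL) and are read in marked tubes, which limits discretion over removal. A participant's own taste report can unmask the 15-minute and later steps whether or not a code exists. Nor can it be shown that the back-ups have blinded duties.

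All of this stands and narrows the point. It does not remove the contradiction: three sections direct that the assignment go to blinded staff, and none limits it to a safe form.

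**Conclusion.** The concern holds as a contradiction in the masking procedure. As written, the plan discloses the group assignment to staff it calls blinded, before any sample is taken, and leaves its form undefined. Masking fails directly if the form is a product name or the Experimental/Control label, and is fragile if it is a shared code. It is preserved only if the form is a participant-unique number.

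The exposure that this adds, beyond what a participant's own remarks would reveal anyway, is mainly in the baseline sample, supervision of the rinse, T0 collection and removal decisions at those two points. Under a shared code and q = 0.1, about 88% (84 per arm) or 82% (55 per arm) of an arm would be sampled after its code was known. This illustrates reach; no bias in infectivity or RNA level is shown, and assay reading stays masked.

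It should be fixed. Confidence is moderate, because both the recipient and the form of the code have to be inferred.

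**What to change.** In Sections 3, 6.2.2 and 9.2, replace the communication of the group assignment with wording to this effect: the unblinded person hands blinded staff only the pre-aliquoted rinse, marked with a study ID unique to the participant; no product name, group label or shared group code is given to anyone who supervises the rinse, collects saliva, decides on removal or gives the survey. Align Section 6.2.3 and the container descriptions, which now call it unlabelled in some places and refer to a code associated with the syringe in another. Keep the schedule look-up in Section 9.2 for emergency unblinding.

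In Section 3, replace the description of a single unblinded person with an unblinded role and designated back-ups. State that a back-up who has prepared rinses takes no further part in sampling, removal decisions or surveys.

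The cost is protocol wording and an ID label on each container. The one practical burden is that back-ups must come from staff who do not collect samples. The change does not stop a participant's own taste report from revealing that participant's rinse after it has been used.

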6.2.3 Blinding

At their onsite visit, subjects will be provided with an unlabeled/blinded mouth rinse. The researcher in charge of collecting the salivary samples will be blinded to the mouthwash solution as well, as they will be given a pre-aliquoted mouth rinse in an unlabeled storage syringe to provide to the patient for the rinse. Our statistical consultant, [name], will set up a randomization schedule that the team will abide by for assignment of enrolled subjects.

6.2.4 Follow-up Visits

This study requires only one 70-90 minute, single visit appointment. No diagnostic tests will be run as part of this clinical trial. All participants will already have known COVID+ status. Participants with at-home rapid antigen COVID+ tests will have their COVID infection confirmed with a rapid antigen test administered by study personnel at the time of visit. Results to the rapid antigen test will be available to participants and study personnel 15 minute after being administered. Therefore, no follow-up reporting is needed.

6.2.5 Completion/Final Evaluation

This study requires only one 70-90 minute, single visit appointment. After consenting and randomization, subjects will be asked to rinse with an unlabeled/blinded antiviral mouth rinse for 60 seconds and provide 5 mL of saliva prior to the rinse and 2 mL of saliva immediately post-rinse, 15 minutes post-rinse, 30 minutes post-rinse, 45 minutes post-

rinse, and 60 minutes post-rinse. Subjects will also be asked to complete a short survey about the rinsing experience.

Subjects may withdraw from the trial at any time at their own request, or they may be withdrawn at any time at the discretion of the Investigator or Sponsor for safety, behavioral or administrative reasons.

The Investigator may discontinue a subject if, in the opinion of the Investigator, the subject is no longer a suitable candidate for the study. Possible reasons for the discontinuation of a subject are including but not limited to: adverse event, protocol deviation, missed appointment, subject no longer meets the eligibility criteria.

Patients may be removed from the study due to an allergic reaction to a mouth rinse or due to failure or inability to comply with study procedures.

If a patient suffers from severe xerostomia/dry mouth, such that s/he cannot produce the baseline salivary sample volume or the immediate, 15 minute and 30 minute post-rinse saliva volumes, s/he will be removed from the study with a parking voucher, but without a gift card and will be replaced. If a patient suffers from dry mouth, such that s/he cannot produce salivary sample volumes needed for later time points (45 minutes or 60 minutes post-rinse) but s/he produced sufficient baseline, immediate, 15 minute and 30 minute post-rinse samples, s/he will still be compensated with a gift card and parking vouchers, and will remain in the study. Missing or deficient salivary samples will be noted in CDART. Severe xerostomia is an exclusion criteria during screening, yet we anticipate that some individuals may not know that they have severe xerostomia until they are participating in the study visit and then need to discontinue due to reduced salivary flow, as described.

